12.2 Appendix: CTCAE Immune System Hypersensitivity Grades

Table 10. CTCAE Immune System Hypersensitivity Grades

Adverse Event	Grade 1	Grade 2	Grade 3	Grade 4	Grade 5
Allergic reaction Definition: A disort	Transient flushing or rash, drug fever <38°C (<100.4°F); intervention not indicated	interruption indicated; responds promptly to symptomatic treatment (e.g., antihistamines, NSAIDS, narcotics); prophylactic medications indicated for ≤24 hours	Prolonged (e.g., not rapidly responsive to symptomatic medication and/or brief interruption of infusion); recurrence of symptoms following initial improvement; hospitalization indicated for clinical sequelae (e.g., renal impairment, pulmonary infiltrates) or general response fro	Life-threatening consequences; urgent intervention indicated	Death
Anaphylaxis	-	-	Symptomatic bronchospasm, with or without urticaria; parenteral intervention indicated; allergy-related edema/angioedema; hypotension	Life-threatening consequences; urgent intervention indicated	
and histamine-like	substances from m	ast cells, causing a	natory reaction resulting hypersensitivity immunation, cyanosis, and loss of	une response. Clini	ically, it

ADCT-402-102	Protocol Amendment 3

Adverse Event	Grade 1	Grade 2	Grade 3	Grade 4	Grade 5
Autoimmune disorder	Asymptomatic; serologic or other evidence of autoimmune reaction, with normal organ function; intervention not indicated	Evidence of autoimmune reaction involving a non-essential organ or function (e.g., hypothyroidism)	• ,	Life-threatening consequences; urgent intervention indicated	Death
			issue destruction of a individual to his own		
syndrome	reaction; infusion interruption not indicated; intervention not indicated	infusion interruption indicated but responds promptly to symptomatic treatment (e.g., antihistamines, NSAIDS, narcotics, intravenous fluids);	not rapidly responsive to symptomatic medication and/or brief interruption of infusion); recurrence of symptoms following initial improvement; hospitalization indicated for	consequences; pressor or ventilatory support indicated	
Definition: A disor		prophylactic medications indicated for ≤24 hours	clinical sequelae (e.g., renal impairment, pulmonary infiltrates)		

breath; it is caused by the release of cytokines from the cells.

ADCT-402-102 Protocol Amendment 3

Adverse Event	Grade 1	Grade 2	Grade 3	Grade 4	Grade 5
Serum sickness	Asymptomatic;	Moderate	Severe	Life-threatening	Death
	clinical or	arthralgia; fever,	arthralgia or	consequences;	
	diagnostic	rash, urticaria,	arthritis;	pressor or	
	observations	antihistamines	extensive rash;	ventilatory	
	only;	indicated	steroids or	support	
	intervention		intravenous	indicated	
	not indicated		fluids indicated		
discomfort, and dy	/spnea.				
discomfort, and dy	Asymptomatic or	Moderate;	Severe or	Life-threatening	
discomfort, and dy Immune system	Asymptomatic or mild symptoms;	Moderate; minimal, local	Severe or medically	Life-threatening consequences;	
discomfort, and dy Immune system disorders -	Asymptomatic or mild symptoms; clinical or	Moderate; minimal, local or non-invasive	Severe or medically significant but	Life-threatening consequences; urgent	
discomfort, and dy Immune system disorders -	Asymptomatic or mild symptoms; clinical or diagnostic	Moderate; minimal, local or non-invasive intervention	Severe or medically significant but not immediately	Life-threatening consequences; urgent intervention	
discomfort, and dy Immune System disorders -	Asymptomatic or mild symptoms; clinical or diagnostic observations	Moderate; minimal, local or non-invasive intervention indicated;	Severe or medically significant but not immediately life-threatening;	Life-threatening consequences; urgent	
discomfort, and dy Immune system disorders -	Asymptomatic or mild symptoms; clinical or diagnostic observations only;	Moderate; minimal, local or non-invasive intervention indicated; limiting	Severe or medically significant but not immediately life-threatening; hospitalization or	Life-threatening consequences; urgent intervention	
discomfort, and dy Immune system disorders -	Asymptomatic or mild symptoms; clinical or diagnostic observations only; intervention not	Moderate; minimal, local or non-invasive intervention indicated; limiting age-appropriate	Severe or medically significant but not immediately life-threatening; hospitalization or prolongation of	Life-threatening consequences; urgent intervention	
discomfort, and dy Immune system disorders -	Asymptomatic or mild symptoms; clinical or diagnostic observations only;	Moderate; minimal, local or non-invasive intervention indicated; limiting age-appropriate instrumental	Severe or medically significant but not immediately life-threatening; hospitalization or prolongation of existing	Life-threatening consequences; urgent intervention	
discomfort, and dy Immune system disorders -	Asymptomatic or mild symptoms; clinical or diagnostic observations only; intervention not	Moderate; minimal, local or non-invasive intervention indicated; limiting age-appropriate	Severe or medically significant but not immediately life-threatening; hospitalization or prolongation of existing hospitalization	Life-threatening consequences; urgent intervention	
discomfort, and dy mmune system disorders -	Asymptomatic or mild symptoms; clinical or diagnostic observations only; intervention not	Moderate; minimal, local or non-invasive intervention indicated; limiting age-appropriate instrumental	Severe or medically significant but not immediately life-threatening; hospitalization or prolongation of existing hospitalization indicated;	Life-threatening consequences; urgent intervention	
antigen. Symptom discomfort, and dy Immune system disorders - Other, specify	Asymptomatic or mild symptoms; clinical or diagnostic observations only; intervention not	Moderate; minimal, local or non-invasive intervention indicated; limiting age-appropriate instrumental	Severe or medically significant but not immediately life-threatening; hospitalization or prolongation of existing hospitalization	Life-threatening consequences; urgent intervention	

Abbreviations: **ADL**, Activities of daily living; **NSAIDs**, non-steroidal anti-inflammatory drugs. Adapted from CTCAE 4.0 – June 14, 2010, Immune system disorders.

ADL

## **1 Introduction**

This statistical analysis plan (SAP) describes the statistical methods to be used during the reporting and analyses of data collected under ADC Therapeutics (ADCT) Protocol ADCT-402-102.

This SAP should be read in conjunction with the study protocol and case report form (CRF).

## **2 Study Objectives**

Refer to the corresponding section in the protocol.

### **3 Study Design**

Refer to the corresponding section in the protocol.

#### **3.1 Sample Size Consideration**

Refer to the corresponding section in the protocol.

#### **3.2 Randomization**

This study is not randomized.

#### **3.3 Modifications to the statistical section of the protocol**

The trial was terminated early, prior to the completion of dose escalation (part 1).” Therefore, only Part 1 data will be analyzed and a selected or modified analysis from the statistical section of the protocol will be performed. Please see details in each section.

## 4 Statistical methods

All analyses use SAS® version 9.4 or higher. Summary tables will be organized by each dose level; if some dose levels have only a few subjects, then dose levels can be combined into dose ranges. All available data will be used in the analyses, and important data will be included in data listings, sorted by dose level, subject, and by visit within subject. Missing data will not be imputed, except via censoring in survival analyses and as otherwise specified.

Unless otherwise noted, categorical data will be presented using counts and percentages, with the number of subjects in the analysis set by treatment group as the denominator for percentages. Percentages will be rounded to one decimal place, except 100% will be displayed without any decimal places, and percentages will not be displayed for zero counts. Continuous data, unless otherwise noted, will be summarized using the number of observations (n), mean, standard deviation (std), median, minimum, and maximum. Minima and maxima will be rounded to the precision of the original value, and means, medians, and confidence intervals (CIs) if presented will be rounded to 1 decimal place greater than the precision of the original value. The std will be rounded to 2 decimal places greater than the precision of the original value, up to a maximum of 3 decimal places.

No hypothesis testing will be performed in this study.

### 4.1 Analysis Sets

#### 4.1.1 Safety Analysis Set

The safety analysis set consists of all subjects who receive ADCT-402.

### 4.2 Subject Disposition

For the Safety analysis set, the number and percentage of subjects who discontinued study treatment and discontinued the study for each reason will be tabulated for each dose level.

Subject disposition data will be listed.

The number and percentage of patients with any important clinical study report (CSR) reportable protocol deviation will be summarized overall and by type of deviation. The pre-defined important CSR reportable protocol deviations are listed below; in addition, any other protocol deviations deemed by ADCT medical to be important CSR reportable deviations will be included in the summary.

1. Patient entered the study even though they did not satisfy the entry criteria
2. Patient received an excluded concomitant treatment
3. Patients who developed withdrawal criteria during the study but were not withdrawn.  
The withdrawal criteria include:
  - Grade 3 or higher hypersensitivity reaction
  - a recurrent Grade 3 or 4 toxicity, excluding hematological toxicity
  - a protocol-defined dose-limiting toxicity (DLT) beyond Cycle 1 (except in the case of potential patient benefit, which must be approved by the Sponsor)
  - a dosing delay >21 days (except in case of potential patient benefit, which must be approved by the Sponsor)

- toxicity recurs at the 2nd reduced dose level and at a severity that would mandate a treatment withdrawal
- 4. Patient who received the wrong treatment or incorrect dose. For example,
  - actual dose of study drug was more than 15% greater than protocol defined planned dose level, at any of dose administration
  - patient started next cycle less than 18 days later after Day 1 of the most recent treatment cycle

### 4.3 Demographic and Baseline Characteristics

Demographic and baseline characteristics will be tabulated for the Safety analysis set.

Variables include the following:

- Sex (female, male)
- Race (white, black or African-American, Asian, American Indian or Alaska native, native Hawaiian or other Pacific Islander, other)
- Ethnicity (Hispanic or Latino, not Hispanic or Latino)
- Age (years)
- Age group (< 65, ≥ 65 - < 75, ≥ 75 years)
- Height (cm)
- Weight (kg)
- Body mass index (kg/m^2)
- ECOG PS

Demographic and baseline characteristics data will be listed.

### 4.4 Pre-treatment disease characteristics and medical history

Cancer history will be summarized for the Safety analysis set. Cancer history will be listed and the following variables will be included:

- Date of initial diagnosis of B-ALL
- Current disease status (primary refractory, relapsed)
- Extramedullary involvement and site of involvement

Cytogenetic analysis data will be summarized, and the following variables will be included:

- ALL with t(9;22)(q34;q11.2); BCR-ABL (Philadelphia chromosome)
- ALL with t(v;11q23) (MLL rearranged)
- ALL with t(1;19)(q23;p13.3); TCF3-PBX1 (E2A-PBX1)
- ALL with t(12;21)(p13;q22); ETV6-RUNX1 (TEL-AML1)
- Hyperdiploid > 50
- Hypodiploid
- t(5;14)(q31;q32); IL3-IGH

All cytogenetic analysis data will be listed.

Bone marrow evaluation (bone marrow aspirate and/or bone marrow biopsy) at screening will be listed.

Medical history will be summarized by system organ class and preferred term. All medical history data will be listed.

#### **4.5 Prior anticancer therapy**

The number and percent of patients who had prior stem cell transplant and radiotherapy will be summarized.

The number of lines of prior systemic therapies will be summarized. Number of lines is derived from the unique number of regimen number reported on the prior systemic treatment CRF page and the mobilization treatment and/or conditioning treatment from the prior stem cell transplant, if appropriate.

Prior stem cell transplant, radiotherapy and systemic therapy data will be listed.

#### **4.6 Prior or Concomitant Medications (other than anticancer therapies)**

Prior and concomitant medications will be coded using the World Health Organization-Drug Dictionary (WHO-DD).

Patient listing of all prior and concomitant medications will be provided. Pre-medication for dosing (for example, prophylaxis for hypersensitivity) will listed separately.

#### **4.7 Exposure to Treatment**

##### **4.7.1 Extent of ADCT-402 Exposure**

ADCT-402 exposure will be summarized for the Safety analysis set by dose level. The following items will be tabulated.

- Duration of treatment (in weeks) = (date of last dose – date of first dose +1)/7
- Number of infusions
- Cumulative dose (in ug/kg) = sum of (dose administered at each infusion [ug] /last available weight before each infusion[kg])  
 where dose administered at each infusion[ug]=  
 concentrated IP volume [ in mL]\* 5 mg/mL \*1000 or serially diluted IP volume[ in mL]/50\* 5 mg/mL \*1000; or  
 for partial infusion, multiply by (1- volume of dosing solution not administered [in mL]/ 50 mL)
- Relative dose intensity (%) = (Cumulative dose / (Duration of treatment + 6/7 for QW or + 20/7 for Q3W))/ planned weekly dose intensity \*100%  
 where planned weekly dose intensity =  
 planned dose level at cycle 1 day 1 for QW, or

planned dose level at cycle 1 day 1 ÷3 for Q3W, for example, =10 ug/kg for 30ug/kg Q3W planned dose level.

Relative dose intensity will be additionally presented categorized (<60%, >=60 - <80%, >=80 - <90%, >=90 - <110%, >=110%) Exposure data and infusion details will be listed together.

## **4.7.2 Subsequent Anticancer Therapy or Procedure**

Subjects' subsequent anticancer therapy or procedure including systemic therapy, radiation, or other, along with the start date of subsequent anticancer therapy or procedure will be listed.

## **4.8 Safety Analyses**

### **General common rules**

All safety analyses will be performed on the safety analysis set, unless otherwise specified, using the following common rules:

- The baseline value will be defined as the last non-missing value or measurement taken up to the first dose of the study drug
- The analysis of the safety variables will be essentially descriptive and no systematic testing is planned.
- If relevant, selected safety analyses may be summarized by age, sex, racial subgroups, and any pertinent subgroups.
- The toxicity grade according to the Common Terminology Criteria for Adverse Events (CTCAE) version 4.0 will be taken into account in the summary. For subjects with multiple occurrences of the same event, the maximum grade will be used. If a subject has both missing and non-missing severity grades for treatment-emergent adverse events (TEAEs) within the same preferred term (PT), the missing severity of the TEAE will be treated as a lower severity grade (ie, the subject will be counted under the non-missing severity grade).

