6.3.3.3 Reporting Adverse Events

All AEs reported or observed during the study will be recorded on the AE page of the eCRF. Information to be collected includes drug treatment, dose, event terminology, date of onset, CTCAE Version 4.0 assessment of severity and relationship to study drug, date of resolution of the event, seriousness, any required treatment or evaluations, and outcome. With the exception of disease progression, AEs resulting from concurrent illnesses, reactions to concurrent illnesses, and reactions to concurrent medications also must be reported. All AEs will be followed to adequate resolution. CTCAE Version 4.0 will be used to grade all AEs (Section 6.3.3.4).

Any AE that meets SAE criteria (Section 6.3.3.1) must be reported to the contract research organization (CRO) immediately (i.e., within 24 hours after the time site personnel first learn about the event). The following contact information is to be used for SAE reporting:

ADCT-402-102 Protocol Amendment 3

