6.3.3.4 Assessment of Severity

Adverse events will be graded according to CTCAE Version 4.0. For events not included in the CTCAE criteria, the severity of the AE is graded on a scale of 1 to 5, as shown in Table 3.

Table 3. Definition of Severity Grades for Common Terminology Criteria for Adverse Events (CTCAE)

Grade	Definition
1	Mild; asymptomatic or mild symptoms; clinical or diagnostic observations only; intervention not indicated
2	Moderate; minimal, local or non-invasive intervention indicated; limiting age-appropriate instrumental ADL ^a
3	Severe or medically significant but not immediately life-threatening; hospitalization or prolongation of hospitalization indicated; disabling; limiting self-care ADL ^b
4	Life-threatening consequences; urgent intervention indicated
5	Death related to adverse event

a Instrumental activities of daily living (ADL) refer to preparing meals, shopping for groceries or clothes, using the telephone, managing money, etc.

Changes in the severity of an AE should be documented to allow an assessment of the duration of the event at each level of intensity to be performed. Adverse events characterized as intermittent do not require documentation of onset and duration of each episode.

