### **4.8.2 Adverse Events, Serious Adverse Events, and Deaths**

#### **4.8.2.1 Analyses of adverse events**

The primary focus of adverse event reporting will be on the TEAEs. A TEAE is defined as an adverse event (AE) that occurs or worsens in the period from the first dose of study drug up to 84 days after the last dose of study drug, or start of new anti-cancer therapy, whichever is earlier.

If an AE date/time of onset (occurrence, worsening, or becoming serious) is incomplete, an imputation algorithm will be used to classify the AE as pre-treatment, TEAE, or post-treatment. For example, if only the day of the AE onset is missing, the year and month will be compared with the first dose and 84 days after the last dose of study drug, or start of new anti-cancer therapy, whichever is earlier. And if the month and day of the AE onset are missing, the year will be compared with the first dose and 84 days after the last dose of study drug, or start of new anti-cancer therapy, whichever is earlier. The algorithm for imputing TEAE will be conservative and will classify an AE as a treatment emergent unless there is definitive information to determine it is non-TEAEs.

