## 6 Data handling conventions

### 6.1 General conventions

#### 6.1.1 Missing data

##### Handling of missing relationship to investigational product of AEs

If the assessment of the relationship to investigational product is missing, then the relationship to investigational product has to be assumed and the AE considered as such in the frequency tables of possibly related AEs, but no imputation should be done at the data level.

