##### Handling of missing severity/grades of AEs

If the severity/grade is missing for one of the treatment emergent occurrences of an AE, the maximal severity of the remaining occurrences will be considered. If the severity is missing for all the occurrences a “missing” category will be added in summary table.

No other imputation of values for missing data will be performed.

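### An ungraded fatal or life-threatening TEAE is not counted as Grade 3 or higher for its preferred term unless another occurrence of that term is graded 3 or higher

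*SAP*

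**What the plan says.** **How the grade is chosen.** SAP 4.8 (General common rules) sets the basic rule: "For subjects with multiple occurrences of the same event, the maximum grade will be used". When grades are partly missing within a preferred term, "the missing severity of the TEAE will be treated as a lower severity grade", which the SAP explains as "the subject will be counted under the non-missing severity grade". SAP 6.1.1 repeats this for an ungraded treatment-emergent occurrence: "the maximal severity of the remaining occurrences will be considered". If every occurrence is ungraded, 6.1.1 adds a missing category to the table. It then rules out any further imputation, so a programmer following the SAP could not infer a grade from the outcome.

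**Where the grade is used.** SAP 4.8.2.1 tabulates all, related, serious, and Grade 3 or higher TEAEs by maximum grade. Its overview has one row for TEAEs of Grade 3 or higher and a separate row for TEAEs that led to death.

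**What the protocol records.** Protocol 6.3.3.3 collects, for each event, severity and causality as well as "date of resolution of the event, seriousness, any required treatment or evaluations, and outcome". Protocol 6.3.3.4, Table 3, places life-threatening consequences at Grade 4 and defines Grade 5 as "Death related to adverse event".

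**The concern.** For the worst events, a missing grade need not be unknown. A fatal outcome or a life-threatening seriousness criterion already points to Grade 5 or 4 on the protocol's own scale. The SAP nevertheless assumes that the ungraded occurrence was the milder one, so the rule can understate a patient's maximum grade even where other recorded data contradict it.

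The direction also differs from the SAP's two other rules for incomplete adverse event data. For missing causality, "then the relationship to investigational product has to be assumed" (SAP 6.1.1). For incomplete onset dates, the algorithm "will classify an AE as a treatment emergent unless there is definitive information" to the contrary (SAP 4.8.2.1). Only missing grade is resolved in the less cautious direction.

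Safety is a primary endpoint (protocol 7.2.1). The trial stopped before dose escalation was complete (SAP 3.3), and DLTs and efficacy are only listed (SAP 4.8.1 and 4.9). The TEAE tables by grade are therefore among the main summarised results.

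**Working it through.** The documents give no figure for missing grades, so there is no stated number to reproduce. The check is to run the rule through every case.

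**Inputs.** The rule comes from SAP 4.8 and 6.1.1. The grades of the ungraded event are those that Table 3 gives for a life-threatening event (4) and a fatal one (5). The patient's highest other grade for the same preferred term is none or 1 to 5. That makes 6 × 2 = 12 combinations.

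| Highest other grade for the term | SAP counts the patient at | In the Grade 3 or higher row for the term? | Maximum if the outcome set the grade (life-threatening / fatal) |
|---|---|---|---|
| none | missing | no | 4 / 5 |
| 1 | 1 | no | 4 / 5 |
| 2 | 2 | no | 4 / 5 |
| 3 | 3 | yes | 4 / 5 |
| 4 | 4 | yes | 4 / 5 |
| 5 | 5 | yes | 5 / 5 |

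**Result by preferred term.**
- In 3 × 2 = 6 of the 12 combinations (other grade none, 1 or 2) the patient is not counted as Grade 3 or higher for the term.
- In 3 of the other 6 the patient stays in the row but the maximum is too low: Grade 3 shown instead of 4, 3 instead of 5, and 4 instead of 5.
- In the last 3 nothing changes.

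These are counts of cases, not probabilities.

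**The all-ungraded case.** The rule about a lower grade does not apply here. The patient goes to the missing category, and the SAP does not say whether that category is shown in the Grade 3 or higher table.

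**Result in the overview.** The overview row for Grade 3 or higher takes in all terms. A patient is lost from it only with no Grade 3 or higher TEAE of any term. When that holds and the ungraded event was fatal, the patient counts in the row for fatal TEAEs but not in the row for Grade 3 or higher, although a fatal event is Grade 5 by definition.

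**Size per patient.** One patient changes an incidence by 100/n percentage points:
- n = 3: 33.3
- n = 6: 16.7
- n = 10: 10.0
- n = 40: 2.5

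The first two are the 3+3 cohort sizes, 10 is the usual cap per dose level (protocol 3.2), and 40 is the planned Part 1 maximum (protocol 7.3). SAP 4 allows sparse dose levels to be combined, which would make the change smaller.

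**The case against.** The strongest reply is that little is lost in practice. SAP 4.8.2.1 also has overview rows for serious and fatal TEAEs, a table of serious TEAEs, and listings of all AEs, all SAEs and all fatal TEAEs. SAP 4.8.2.2 summarises deaths. With 3 to 6 patients per dose level, a reader can follow each patient in the listings. Severity is a required field, SAEs are reported within 24 hours, and eCRFs are checked for completeness (protocol 6.3.3.3 and 7.7), so an ungraded fatal event should be rare. Dose decisions belonged to the steering committee (protocol 6.3.2), and no hypothesis is tested. All of this stands. It limits the consequence but does not remove the disagreement between tables.

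It can also be said that a five-level grade, unlike relatedness or treatment emergence, has no natural cautious default. That is fair for most ungraded events, and the current rule can stay for them. It does not apply where outcome or seriousness already indicates the grade.

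A reader might infer that hospitalisation should likewise set Grade 3. The documents do not support this. Table 3 applies to events not included in the CTCAE criteria, and hospitalisation is a seriousness criterion (protocol 6.3.3.1), so a hospitalised event is not necessarily Grade 3. The mapping for life-threatening and fatal events is firmer: the CTCAE excerpt in protocol Appendix 12.2 also puts life-threatening consequences at Grade 4 and death at Grade 5.

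**Conclusion.** The point holds in a limited form. The SAP can tabulate an ungraded fatal or life-threatening TEAE at Grade 1 or 2, or as missing, and the overview rows can then disagree. This conflicts with the protocol scale and is less conservative than the SAP's own handling of missing causality and onset.

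Two broader readings are tempting but unsupported. One is that an ungraded event can never reach the Grade 3 or higher tables; a patient with another occurrence of the term at Grade 3 to 5 stays in the row. The other is that severe events are hidden; they remain in the serious, fatal and death outputs.

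The number of patients affected cannot be estimated, because the documents give no rate of missing grades. An estimate would also have to require that the event was fatal or life-threatening and that no other occurrence was graded 3 or higher. It could not take the planned 40 patients as given, since the trial stopped early. The number is probably small, and the size per patient is as shown above.

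The conclusion assumes that the life-threatening criterion is recorded separately. The protocol says seriousness is collected, but the case report form is not among the documents. The fatal case needs only the outcome field.

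**What to change.** Change SAP 4.8 and the missing-grade paragraph of SAP 6.1.1, for tables only:

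- Before the patient's maximum is taken, count an ungraded TEAE with a fatal outcome as Grade 5, and an ungraded TEAE recorded as life-threatening as Grade 4.
- Keep the current rule for all other ungraded TEAEs, including those serious only through hospitalisation. Add a footnote with their number and how many were serious.
- Word the closing ban on other imputation in 6.1.1 so that it allows this exception. The data themselves stay unchanged.

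The cost is two SAP sentences and a few lines of code. The downside is that Grade 3 or higher counts may rise slightly. If the database is still open, querying the missing grades first would leave the rule with little to do.
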